8.2.1. Sensitivity Analyses of Primary Endpoint

Missing Data: The following sensitivity analyses will be conducted on the primary efficacy endpoint to assess the impact of missing data on study conclusions:

- **Last Observation Carried Forward (LOCF):** Post-baseline missing DUX4 score will be imputed using baseline DUX4 score for each subject with missing data. Patients who are missing the baseline assessment will be excluded from the analysis.
- **Placebo Mean Imputation:** Post-baseline missing DUX4 score will be imputed using mean post-baseline score calculated from the placebo arm. Patients who are missing the baseline assessment will be excluded from the analysis.
- **Observed worst case imputation:** For subjects with missing baseline DUX4, imputation will be done using the smallest baseline DUX4 score among subjects with non-missing data. For subjects missing post-baseline DUX4, imputation will be done using the highest DUX4 score among subjects with non-missing data.

DUX4 by timepoint: The primary endpoint will be analyzed separately for Week 16 and Week 36 to assess the impact of biopsy timing on study conclusions.

COVID-19 related treatment disruptions: Subjects may be diagnosed with COVID-19 and proceed on a quarantine or have no access to study treatment for a prolonged duration. These subjects will be excluded from analysis of the primary endpoint, to assess the impact of COVID-19 related treatment disruptions on the study conclusions.

Excluding cross-over subjects: Subjects who already transitioned into open label losmapimod based on the prior protocol version will be excluded from the analysis.

DUX4 change excluding subjects with censored laboratory observations at baseline:
Subjects with censored observations at baseline for any of the transcripts in the panel of 6 DUX4-regulated transcripts will be excluded from the analysis.

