3.1. Overall Study Design and Plan

This study will be conducted in 2 parts: a randomized, double-blind placebo-controlled treatment period for 48 weeks, followed by a losmapimod open-label treatment period with a study population of males and females between 18 and 65 years of age at enrollment, inclusive, who have confirmed diagnosis of FSHD1 with 1 to 9 repeats via assessment of the size of the D4Z4 array on chromosome 4; a clinical severity score of 2 to 4 (RICCI score; range 0-5), inclusive, at screening; and a MRI eligible muscle for biopsy, as determined by a central reader.

During the placebo-controlled treatment period, approximately 76 subjects with FSHD1 will be randomized 1:1 to receive 15 mg PO of losmapimod (n=38) or placebo (n=38) tablets BID for 48 weeks. At the time of the latest protocol amendment (Version 4.0; 10Apr2020), enrollment was completed, a total of 80 subjects have been enrolled.

Once subjects reach Week 48, they will have the option to roll over into the open-label extension, with all subjects receiving 15 mg losmapimod PO BID. Subjects who wish to roll over into the

open-label extension must complete all procedures from the Week 48 end of placebo-controlled treatment period/start of open-label extension visit. Prior to the COVID-19 pandemic, subjects who reached the Week 24 visit had the option to roll over into the OLE. Subjects who have already rolled over to the OLE prior to the COVID-19 pandemic (n=12) will remain on open label treatment. Their next clinic visits will follow the assessments for the Week 36 and Week 48 visits in the placebo-controlled portion of the study in the COVID-19 Pandemic Emergency protocol version 4.0. These subjects will not undergo the Week 36 biopsy. Subjects who did not roll over prior to the COVID-19 pandemic, and thus are still on the randomized treatment, will continue on the randomized treatment and roll over into the OLE at the Week 48 visit. Please see the COVID-19 Pandemic Emergency protocol version 4.0 for further details.

[figure not shown]
The placebo-controlled treatment period will include a 4-week screening period and a 24 or 48-week placebo-controlled treatment period. Subjects who rolled over to the OLE portion of the study prior to the COVID-19 pandemic (under protocol version 3.0) have completed a 4-week screening period followed by a 24-week placebo-controlled treatment period.

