4.7. Sample Size

Assuming an effect size of 0.70, a sample size of 68 subjects (34 subjects per group) will be needed to provide 80% power with a 2-sided test at a 0.05 significance level to detect a difference between losmapimod and placebo in change from baseline in DUX4 activity in affected skeletal muscle after 16 weeks or 36 weeks (depending upon when the muscle biopsy was performed) during the placebo-controlled treatment period. Assuming that approximately 10% of subjects will be non-evaluable, approximately 76 subjects will be randomly assigned at a 1:1 ratio to losmapimod and placebo (38 subjects per group).

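### The observed-worst-case imputation for DUX4 treats both arms alike, so it is not a worst case for losmapimod and can strengthen the result it should stress

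*SAP*

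**What the plan says.** SAP 8.2.1 lists three analyses to assess the effect of missing data on the primary endpoint.

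- **LOCF:** "Post-baseline missing DUX4 score will be imputed using baseline DUX4 score for each subject with missing data", which sets that subject's change to zero.
- **Placebo mean:** "Post-baseline missing DUX4 score will be imputed using mean post-baseline score calculated from the placebo arm", which is one constant for every missing subject in either arm.
- **Observed worst case:** for a missing baseline, "imputation will be done using the smallest baseline DUX4 score among subjects with non-missing data"; for a missing post-baseline score, "For subjects missing post-baseline DUX4, imputation will be done using the highest DUX4 score among subjects with non-missing data".

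Neither half of the worst-case rule names an arm, and the SAP addendum does not change it. SAP 15.8 plans all three analyses for both the FAS and the PPS. The primary ANCOVA itself uses available data (Protocol 7.6.2), and an unavailable result counts as missing (SAP 8.2).

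**The concern.** A worst-case analysis should ask whether the conclusion survives when missing data are resolved against the drug. Here placebo subjects also receive the unfavourable value, so the direction of the stress depends on which arm has more missing biopsies. If placebo has more, the analysis adds to the apparent benefit and could be reported as evidence of robustness.

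The three imputations are the only analyses planned specifically for missing biopsies, on the endpoint that opens the testing sequence in SAP 8.1. Missing biopsies are a real prospect. SAP 4.7 allows for about 10% non-evaluable, Protocol 3.2.2 reports many missed Week 16 visits, and withdrawals are not replaced (Protocol 4.2.3).

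**Working it through.** **1. The plan's own figure.** SAP 4.7: "Assuming an effect size of 0.70, a sample size of 68 subjects (34 subjects per group) will be needed" for "80% power with a 2-sided test at a 0.05 significance level". The two-sample t-test at effect size 0.70 has power 0.7997 with 33 per group and 0.812 with 34, so 34 is confirmed. Then 68/0.90 = 75.6, giving 76, or 38 per arm. Ten per cent of 76 is 7.6, so about 8 missing biopsies is the plan's own allowance.

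**2. Assumptions not in the documents.** Normal scores with unit SD; baseline/post-baseline correlation 0.5, so the SD of change is √(2 − 2×0.5) = 1; biopsies missing completely at random within arm; the split of missing biopsies between arms (written losmapimod/placebo); the highest score taken from observed post-baseline values; higher is unfavourable, as the rule implies.

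**3. Expected worst-case estimate.** Take n per arm, m_L and m_P missing, true effect −δ and imputed value M. The losmapimod mean is [−δ(n − m_L) + m_L·M]/n and the placebo mean is m_P·M/n. The difference is

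−δ(n − m_L)/n − M(m_P − m_L)/n.

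M is the expected maximum of n − m_P draws from N(0,1) and n − m_L draws from N(−δ,1), found by numerical integration.

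| True effect | Missing | M | Arithmetic (n = 38) | Estimate |
|---|---|---|---|---|
| 0 | 2/6 | 2.37 | −2.37×4/38 | −0.25 |
| 0 | 2/8 | 2.36 | −2.36×6/38 | −0.37 |
| 0 | 4/4 | 2.37 | −2.37×0/38 | 0 |
| −0.70 | 2/6 | 2.13 | −0.70×36/38 − 2.13×4/38 = −0.663 − 0.224 | −0.89 |
| −0.70 | 4/4 | 2.15 | −0.70×34/38 | −0.63 |
| −0.70 | 6/2 | 2.17 | −0.70×32/38 + 2.17×4/38 = −0.589 + 0.228 | −0.36 |

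Simulating the SAP's ANCOVA (4,000 trials per setting) reproduces these values. With 40 per arm and correlations of 0.3 to 0.7, the 2/6 estimate runs from −0.20 to −0.31 under no effect and from −0.85 to −0.95 under a true −0.70.

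**4. Worst-case standard error.** Under no effect at 4/4, the model SE is 0.257 and the sampling SD of the estimate is 0.192. The ratio is 0.257/0.192 = 1.34, and rejection is about 1%.

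**5. Placebo-mean rule, no effect.** At 2/8 the model SE is 0.190 and the sampling SD 0.210; 0.190/0.210 = 0.90, so the SE is about 10% too small. Rejection is 7.2 to 7.6%. At 0/8 the SE is 11% too small and rejection is 7.9%. At 4/4 rejection is 5.2%, about right.

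**6. LOCF.** Its model SE matches its sampling SD in these settings.

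**7. If a higher score were favourable.** The pattern mirrors. With 40 per arm, a true −0.70 and 6/2 missing, the estimate is −0.88. Under either sign, some imbalance favours losmapimod.

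**The case against.** The strongest reply is that the imbalance is set by hand. If 8 missing biopsies fall at random across 76 subjects, losmapimod has 2 or fewer with probability 13%; with 10 missing, 4.3%. Averaged over random splits, the worst-case rule shows no bias and rejects 5.0% (8 missing) or 5.5% (10 missing). Treatment is blinded, the documented cause of missed biopsies is site closure and travel limits, the Week 36 fallback reduces the loss, and any imbalance will be visible when results are read. This stands: the shifts are conditional on a split that the documents give no reason to expect. It does not make the rule a worst case for the drug.

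Three stronger readings are tempting, and the documents do not support them.

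- A reader might infer a false-positive rate of 21 to 23%. That is the worst-case rejection rate at 2/8 only, and no claim of significance rests on this analysis (SAP 8.1 and 8.2).
- A reader might infer that the rule cannot challenge a positive result. It can: at 4/4 with a true −0.70, rejection falls from about 90% on observed data to about 67 to 71%, and at 6/2 the rule works against losmapimod.
- A reader might infer that all three analyses impute means and give standard errors that are too small. Only one imputes a mean, LOCF is not affected in this way, and the worst-case SE is too large.

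The normalisation appendix was not available for this review, so the score's direction may already be defined there. The point is to confirm it in the rule, not to claim that it is missing.

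**Conclusion.** The point holds in a limited form. The worst-case rule is neutral between arms and does not test the conclusion against losmapimod. When placebo loses more biopsies it moves the estimate toward losmapimod, by about 0.25 SD at 2/6 and 0.37 SD at 2/8, and it turns a true −0.70 into about −0.89 at 2/6. When missingness is balanced it is unbiased under no effect, with an SE about one third too large. The placebo-mean rule is a lesser matter: a single fixed value that ignores baseline, with an SE about 10% too small when placebo loses most of the missing biopsies and about right when the arms lose equally.

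The sizes rest on the assumptions in step 2, above all the split. Enrolment reached 80 ("a total of 80 subjects have been enrolled"); using 40 per arm changes little. The primary ANCOVA and its p-value are untouched, so this is an improvement that should be made to the sensitivity analyses, not a flaw in the main test.

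**What to change.** 1. Replace or supplement the observed worst case with a delta-adjusted tipping-point analysis directed at losmapimod. Make missing losmapimod values progressively less favourable and report the shift at which the conclusion changes. Impute missing placebo values multiply from the placebo model (baseline DUX4, repeat category) and combine by Rubin's rules. Do not give missing placebo subjects the fixed placebo mean, because that repeats the single-imputation fault.
2. Replace the single placebo-mean imputation with the same reference-based multiple imputation. At 40 per arm, correlation 0.5, a true −0.70 and 4/4 missing, both give an estimate of −0.64, with an SE of 0.209 instead of 0.191.
3. Confirm in the rule that a higher Score 1 is the unfavourable direction. If the worst-case analysis is kept, label it as the same for both arms, state which visits supply the highest score, and show missing counts by arm beside it.

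The cost is SAP wording and modest programming, with no new data. The downside is a somewhat less favourable sensitivity result.

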8.3. MSK MRI Muscle Fat Fraction, Lean Muscle Volume and Muscle Fat Infiltration

Measurement of the extent of skeletal muscle tissue replacement by fat in FSHD patients will be done through automatic skeletal muscle segmentation for the 3D muscle volumes and fat fraction analysis via robust algorithms using Dixon imaging. This will be assessed at Screening, Week 12, and Week 48.

A. Composite measures: Composite variables, incorporating pre-selected muscles, will be derived for longitudinal analysis of muscle fat fraction, lean muscle volume and muscle fat infiltration (MFF_{tot} , LMV_{tot} , and MFI_{tot} respectively), as described in [Appendix 15.6](#). The scores will be derived by scientists at the MRI Service Provider (AMRA Medical Inc.) in a blinded fashion, with no access to treatment assignment information.

For each treatment, descriptive statistics of MFF_{tot} , LMV_{tot} , and MFI_{tot} per visit as well as changes from baseline will be presented. A Mixed Effect Model for Repeated Measures (MMRM) model will be used to analyze the change from baseline in each composite MRI score, with repeat number category, treatment group, visit, and treatment-by-visit interactions as fixed effects and baseline value of the parameter as a covariate. Within-group LS mean changes from baseline, the associated SEs and 2-sided 95% CIs, treatment differences in LS mean changes from baseline at Weeks 12 and 48 and the associated 2-sided 95% CIs and 2-sided p-values will be derived from the MMRM model and will be provided in the summary table. An unstructured covariance matrix will be used to model the correlation among repeated measurements within each subject. If models using unstructured covariance do not converge, an AR(1) covariance structured will be used instead. **LMV_{tot} is the key endpoint for hypothesis testing.**

B. Individual Muscles: For each muscle location, a similar method will be used to analyze muscle fat fraction (%), lean muscle volume (L), and muscle fat infiltration (%) per visit as well as changes from baseline.

The LS mean change from baseline by visit of the MSK MRI muscle fat fraction, lean muscle volume, and muscle fat infiltration will be graphically presented.

The change from baseline in the composite parameters will also be summarized by subgroups identified in [Section 4.6](#) to evaluate consistency of treatment effects across the subgroups.

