Blood samples for PK (losmapimod concentrations) endpoints will be collected at Day 1, Week 4, Week 16, and Week 36 at the following time points: immediately predose and 4 hours (± 30 minutes) after administration of the study dose. Pharmacokinetic samples will also be taken, when feasible, after dosing during the Week 12, Week 24, and Week 48 visits, preferably ≥ 1 hour after dosing. Blood samples for target engagement will be collected at Day 1, and Week 16 or Week 36, at the following time points: immediately predose and 4 hours (± 30 minutes) after administration of the study dose. Serum and plasma samples taken at baseline (Day 1; predose) and at Weeks 4, 12, 16, 24, 36, and 48 (predose or postdose) will be used to aid in the discovery of potential biomarkers of FSHD disease activity and treatment effects.

Fulcrum Therapeutics

Losmapimod

Protocol FIS-002-2019, Version 4.0 (COVID-19 Pandemic Emergency Amendment)

10 April 2020

[figure not shown]
Musculoskeletal MRIs will be performed at screening, Week 12, and Week 48. Muscle biopsies will be taken at Day 1 and Week 16 or Week 36, if the muscle biopsy could not be performed at Week 16 due to the COVID-19 pandemic. In skeletal muscle, change from baseline in aberrant DUX4 activity, losmapimod concentrations, and target engagement will be evaluated at Day 1 and Week 16 or Week 36. A portion of the muscle biopsies may be used to aid in the discovery of potential biomarkers of FSHD disease activity and treatment effects.

Safety and tolerability will be evaluated based on the assessment of AEs, AEs of special interest (AESIs), SAEs, laboratory tests, ECGs, vital signs, and physical examinations.

The full schedule of assessments for the placebo-controlled treatment period is provided in [Table 13-1](#). Scheduled visits may be split over 2 days if required, with a maximum of 5 business days in between visits. Unscheduled visits may be performed if clinically indicated. Subjects can travel for MRI or muscle biopsy if needed, but the use of a study-approved MRI scanner should be consistent during the trial.

A schematic of the study design is presented in [Figure 3-1](#).

Figure 3-1 Schematic of Study Design for the Placebo-Controlled Treatment Period

*Muscle biopsy will be performed at Week 16 or at Week 36 if the biopsy could not be performed at Week 16 due to the COVID-19 pandemic

**MRI may not be possible to perform at Week 12 due to the COVID-19 pandemic

Fulcrum Therapeutics Losmapimod

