Blood samples for pharmacokinetics (losmapimod concentrations) endpoints will be collected at Day 1, Week 4, Week 16, and Week 36 at the following timepoints: immediately pre-dose and 4 hours (± 30 minutes) after administration of the study drug. Blood samples for target engagement will be collected at Day 1 and Week 16 or Week 36 at the following timepoints: immediately pre-dose and 4 hours (± 30 minutes) after administration of the study drug. Musculoskeletal MRIs will be performed at screening, Week 12, Week 24, and Week 48. Muscle biopsies will be taken at Day 1 and Week 16, or at Day 1 and Week 36 if the muscle biopsy could not be performed at Week 16 due to the COVID-19 pandemic.

Safety and tolerability will be evaluated based on the assessment of adverse events (AEs), AEs of special interest (AESIs), serious adverse events (SAEs), laboratory tests, electrocardiogram (ECGs), vital signs, and physical examinations.

A schematic of the study design of the placebo-controlled treatment period is presented in [Figure 3-1](#).

Figure 3-1: Schematic of Study Design

Abbreviations: BID, twice daily; MRI, magnetic resonance imaging; OLE, open-label extension

During the open-label extension, subjects will be asked to attend clinic visits approximately every 12 weeks, and MRI will take place every 24 weeks. Study drug (open-label losmapimod) will be administered BID and should be taken with food. Subjects will remain in the open-label extension until study drug approval or until the study is discontinued by the Sponsor. All subjects who complete or discontinue from treatment will be asked to complete a 7-day safety follow-up period.

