3.2.2. Secondary Endpoints

The secondary endpoints of the placebo-controlled treatment period are as follows:

- Safety and tolerability of losmapimod as defined by the following:
 - Type, frequency, severity, seriousness, and relationship of AEs to losmapimod;
 - Incidence of AESI;
 - Number of subjects who prematurely discontinue study drug due to an AE; and
 - Frequency of clinically significant changes in laboratory test, ECG, vital sign, and physical examination results

- Change from baseline in MFF, LMV, and MFI at Week 12, Week 24 (if applicable) and Week 48;
- Plasma concentrations of losmapimod at Week 4, Week 12, Week 16, Week 24, Week 36, and Week 48;
- Concentrations of losmapimod in skeletal muscle biopsy at steady state at Week 16 or Week 36;
- Target engagement parameters in blood, and skeletal muscle biopsy at Week 16 or Week 36.

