4.4. Visit Windows

In general, data for assessments that are collected by scheduled visits will be mapped to visits that appear in the schedule of assessments per the protocol using the actual study day of assessment. Data mapped to scheduled visits will include all data collected up to the reporting cut-off date and may include withdrawal visits and unscheduled visits.

Visit windows will be continuous from the midpoint between two consecutive study visits and will be dependent on the schedule of assessments for each variable independently. The exception is the Week 16 analysis window, which has been extended to allow for potentially delayed visit due to COVID-19 pandemic. An example of the Vital Signs visit window is given in [Table 4-1](#). Visit windows for each variable will be constructed in the same manner.

Table 4-1: Visit Windows

Study Visit	Scheduled Day	Analysis Window
Baseline	1	≤ 1
Week 4	28	>1 to ≤ 56
Week 12	84	>56 to ≤ 98
Week 16	112	>98 to ≤ 154
Week 24	168	>154 to ≤ 210
Week 36	252	>210 to ≤ 294
Week 48	336	>294 to ≤ 378

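### MRI change at Week 24 is a listed secondary endpoint, but the MRI analysis has no Week 24 visit, and the SAP's own window rule puts a Week 24 scan in Week 12 and lets a scan from Day 211 stand as Week 48

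*SAP*

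**What the plan says.** The current text gives two different lists of MRI visits.

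**With Week 24.** SAP 3.2.2 defines the secondary endpoint as "Change from baseline in MFF, LMV, and MFI at Week 12, Week 24 (if applicable) and Week 48", and Protocol 7.1.2 defines it in the same way. SAP 3.1 states: "Musculoskeletal MRIs will be performed at screening, Week 12, Week 24, and Week 48".

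**Without Week 24.** Protocol 3.1.1 states: "Musculoskeletal MRIs will be performed at screening, Week 12, and Week 48". Protocol Table 13-1 and SAP 15.7.1 agree with this and add an MRI at early termination. SAP 8.3 says of the MRI measures: "This will be assessed at Screening, Week 12, and Week 48". From the repeated-measures model (MMRM) it reports "treatment differences in LS mean changes from baseline at Weeks 12 and 48". Section 5.3 of the SAP addendum refers in general terms to every visit after baseline and adds no Week 24 MRI visit or window.

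**The window rule.** Under SAP 4.4, data are "mapped to visits that appear in the schedule of assessments per the protocol using the actual study day of assessment". "Visit windows will be continuous from the midpoint between two consecutive study visits", and they "will be dependent on the schedule of assessments for each variable independently". Withdrawal and unscheduled visits may be mapped too. Table 4-1 is an example for vital signs. Under SAP 4.5, when several efficacy values fall in one window, the one nearest the nominal day is used.

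**The concern.** Week 24 MRIs were part of the design before version 4.0. Protocol 3.2.2 describes Week 24 MRI data as at risk from the pandemic and moves MRI to Week 48 for subjects who missed Week 24. Some subjects may therefore have a Week 24 scan, and the analysis section gives it no visit. Protocol 3.1.1 reports that 12 of 80 enrolled subjects (15%) rolled over to open-label losmapimod at Week 24. For any of them scanned at that visit, it is the last MRI on randomised treatment.

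Two things are at stake:

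- A listed secondary endpoint has no reported treatment comparison, and Week 24 values may enter the Week 12 level of the model.
- With only two post-baseline MRI visits, the Week 48 window opens very early. SAP 8.1 tests LMV at Week 48 second in the fixed sequence, so an early scan can feed a test under Type I error control.

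**Working it through.** **Inputs.** Nominal days come from SAP Table 4-1: Week 4 = 28, Week 12 = 84, Week 16 = 112, Week 24 = 168, Week 36 = 252, Week 48 = 336. The scheduled MRI visits after baseline are Weeks 12 and 48 (Protocol Table 13-1, SAP 15.7.1). The visit allowance at Week 24 is ±5 days.

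**1. Reproduce Table 4-1.** The upper limit is the midpoint to the next visit. For the last visit it is the nominal day plus half the preceding gap.

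| Visit | Calculation | Result | Table 4-1 |
|---|---|---|---|
| Week 4 | (28 + 84)/2 | 56 | 56 |
| Week 12 | (84 + 112)/2 | 98 | 98 |
| Week 16 | (112 + 168)/2 | 140 | 154 |
| Week 24 | (168 + 252)/2 | 210 | 210 |
| Week 36 | (252 + 336)/2 | 294 | 294 |
| Week 48 | 336 + (336 − 252)/2 | 378 | 378 |

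Five of six match. The sixth is the Week 16 extension that SAP 4.4 declares for pandemic delays, so the rule is read correctly.

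**2. Apply the rule to the MRI schedule.** The cut is (84 + 336)/2 = 210. Week 12 is Day >1 to ≤210, and Week 48 starts at Day 211.

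**3. Place a Week 24 scan.** Day 168 ± 5 is Day 163 to 173, which lies wholly inside the Week 12 window.

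- If a scan nearer Day 84 exists, SAP 4.5 selects that one and the Week 24 scan leaves the by-visit analysis.
- If the Week 12 scan is missing, which the note to Protocol Figure 3-1 anticipates, the Week 24 scan is analysed as Week 12. It is then 168 − 84 = 84 days out of place.

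**4. Place an early scan.** A Day 211 scan maps to Week 48 when no scan lies nearer Day 336. It omits 336 − 211 = 125 days, and 125/336 = 37% of the nominal period. By comparison, FSHD TUG, third in the sequence, has a Week 36 visit. Its Week 48 window opens at Day 295, at most 336 − 295 = 41 days early.

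**5. Add Week 24 under the same rule.** The midpoints are (84 + 168)/2 = 126 and (168 + 336)/2 = 252. A Day 168 scan maps to Week 24, and the earliest day that can count as Week 48 moves from 211 to 253.

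**The case against.** The strongest reply is that SAP 8.3 simply follows the version 4.0 design, which has no Week 24 MRI, and that the qualifier in the endpoint list covers scans already taken. On that view the definite fault is unreconciled wording plus one unreported contrast. The MRI windows are also inferred, because none are printed. A programmer who took the visit list from SAP 3.1 would place Week 24 scans correctly. All of this stands as a limit on certainty. It does not remove the point: SAP 4.4 names the protocol schedule as the basis for mapping, that schedule has no Week 24 MRI, and on either reading SAP 8.3 reports no Week 24 comparison.

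Several stronger readings are tempting, but the documents do not support them:

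- **Week 24 scans are lost.** They leave the by-visit summaries and the model only if a nearer scan exists. SAP 4.1 keeps repeat and additional assessments in the listings.
- **A Week 30 scan counts as Week 48.** Week 30 sits on the boundary. On the Table 4-1 convention it is Day 210, which is Week 12. By the SAP 4.3 study-day formula, exactly 30 weeks after first dose is Day 211, which is Week 48.
- **Every early-termination or unscheduled scan from Day 211 becomes Week 48.** A scan nearer Day 336 takes precedence, and the early-termination MRI is not repeated if one was done in the previous 8 weeks.
- **The Week 48 test is directly distorted by Week 24 scans.** A Week 24 scan labelled Week 12 changes the Week 12 contrast, which is outside the sequence. It reaches Week 48 only indirectly through the model. Nor do the documents give an LMV trajectory from which to say that early scans understate 48-week change.

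Adding Week 24 also does not resolve the analysis of roll-over subjects as randomised after they move to open-label drug.

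**Conclusion.** The point holds. A listed secondary endpoint has no analysis visit, and the stated window rule, applied to the stated schedule, gives a wrong label. A Week 24 scan falls in Week 12, up to 84 days out of place at the nominal day. A scan as early as Day 211 can stand for Week 48 LMV when nothing lies nearer Day 336.

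This rests on two assumptions: that MRI windows are built from the protocol schedule, as SAP 4.4 directs, and that some Week 24 or early scans exist. Their number is not given. The 12 roll-over subjects reached Week 24, but the documents do not say how many were scanned, so 12 should not be read as a count of affected scans. The effect on the LMV estimate cannot be sized from the documents. The change should be made because it is cheap and touches an endpoint in the testing sequence.

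**What to change.** 1. Reconcile the MRI visit list across SAP 3.1, 3.2.2, 8.3 and the schedules of events.
2. Print MRI windows by the SAP's own midpoint rule: Week 12 Day >1 to ≤126, Week 24 Day >126 to ≤252, Week 48 Day >252.
3. Do not borrow the Week 48 limits from Table 4-1. Its bounds of 294 and 378 depend on a Week 36 visit that MRI lacks. They would leave Days 253 to 294 unassigned and could exclude delayed Week 48 scans after Day 378.
4. Report Week 24 change by treatment group, in the MMRM if there are enough scans and descriptively otherwise. In either case keep Week 24 scans out of the Week 12 level.
5. Add a sensitivity analysis of Week 48 LMV limited to scans from Day 295 on, the day on which the FSHD TUG window for Week 48 opens.

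The cost is SAP wording, at most one more visit level in the MRI models, and one sensitivity table. There is a small downside. A few scans on Days 211 to 252 would no longer count as Week 48. A sparse Week 24 level may be imprecise or may affect convergence of the unstructured covariance, and the descriptive option in step 4 is there for that case.
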